## Protocol Synopsis (one page)

### Study Title: Teaching Parents Reiki for Their Adolescents Receiving Palliative Care

#### Study Design

##### PICOT:

P: Parents and adolescents receiving palliative care

I: Teaching parents Reiki for use in the home

C: None

O: Primary: The primary outcome for the proposed study is the feasibility and acceptability of teaching Reiki to parents of adolescents receiving palliative care. Secondary outcomes include: adolescent global health, pain interference, medication use, and stress measures of hair cortisol (chronic, long term) and alpha amylase (immediate, short term); and parent symptom profile (depression, anxiety, physical function, pain interference, fatigue, sleep disturbance and ability to participate in social roles and activities), and stress measures of hair cortisol (chronic, long term) and alpha amylase (immediate, short term).

T: Nine weeks from consent through follow up

This intervention is easily implemented across a wide range of geographically dispersed settings. Reiki is a popular complementary health approach across the United States. There are Reiki practitioners in every state according to The International Center for Reiki Training, the largest organization of Reiki practitioners in the country. With a tested protocol, manual, and training, this intervention could be taught to Reiki practitioners and then parents and other caregivers for a reasonably small cost.

#### Significance

Despite advances in the assessment and treatment of symptoms, including adolescents receiving palliative care, parents still report that their children suffer. Adolescents with life-threatening/life-limiting conditions, many of whom are developmentally delayed, experience many symptoms and have complex comorbidities requiring medical management. Many of these adolescents could benefit from complementary health approaches (CHAs) such as Reiki, a gentle light touch biofield energy therapy. Parents of adolescents receiving palliative care also experience high levels of stress. Previous studies have shown that empowering parents in the care of their chronically ill child helps parents better cope with challenges. Preliminary evidence showed that professionally-delivered Reiki is feasible for children and adolescents receiving palliative care at home. The majority of parents in that study said they wished they could learn Reiki so they might provide this relaxing therapy in the moment it was needed rather than waiting for the next professional session.

Teaching parents Reiki has the potential to impact both the child and the parent. Studies with adults have found that professionally-delivered Reiki decreased pain, anxiety, and other symptoms. Parents like to feel empowered in caring for their very ill children and doing so may decrease parental stress and other symptoms. The National Center for Complementary and Integrative Health (NCCIH) considers Reiki to be safe, although little scientific evidence exists about the effectiveness of this intervention. The proposed study addresses NINR priorities of advancing symptom science to “develop [and] test ... novel, scalable symptom management interventions, including CHAs, in real-world clinical settings to improve health outcomes and quality of life”15(p.15) and the science of compassion to improve palliative and end-of-life care through “developing, testing, and implementing personalized, culturally congruent, and evidence-based palliative and hospice interventions . . . that best address the needs of underserved, disadvantaged, and diverse populations across the care continuum.”15(p. 31) A long-term bonus of teaching parents to deliver Reiki is that once learned, Reiki is highly scalable and costs nothing to use, an important potential overall cost savings over other CHAs.

#### Study Schema

See Appendix 2.

## 1 Background and Rationale

Despite advances in the assessment and treatment of symptoms, including pain in adolescents receiving palliative care, parents still report that their children suffer. Advances in medical science and care have led to a growing number of children living with life-limiting chronic conditions. Out of 83 million children under the age of 19, an estimated 600,000 to 1,600,000^17 are living with life-threatening/life-limiting conditions and over 180,000 are considered “medically fragile.” These children require intense medical and nursing care in the home and often experience lengthy, recurrent hospital stays, accounting for about 26% of hospital days and 41% of hospital charges. Adolescents with life-threatening/life-limiting conditions, many of whom are developmentally delayed, experience many symptoms and have complex co-morbidities requiring medical management.

Many of these adolescents could benefit from complementary health approaches (CHAs) such as Reiki, a gentle light touch biofield energy therapy. Parents of adolescents receiving palliative care also experience high levels of stress. Previous studies have shown that empowering parents in the care of their chronically ill child help parents better cope with challenges. Some CHAs show promise for symptom management without side effects, such as sedation from additional medication, thereby permitting greater alertness and allowing more interaction with family and friends. Preliminary evidence from the PI’s pilot study showed that professionally-delivered Reiki is feasible for children and adolescents receiving palliative care at home. The majority of parents said they wished they could learn Reiki so they might provide this relaxing therapy in the moment it was needed rather than waiting for the next professional session. One non-experimental program found that teaching parents Reiki was feasible and acceptable in the hospital. Parents who participated in two or more training sessions felt more confident providing Reiki. During informal interviews, parents said they felt good at being an active participant in their child’s care and that their child experienced increased comfort, relaxation, and decreased pain.

Parents of disabled adolescents receiving palliative care often suffer from high caregiver burden and chronic stress, leading to co-morbidities and decreased QoL. A cross-sectional survey conducted in Europe examined stress in 818 parents caring for a child with cerebral palsy. Results showed that 26% of mothers had very high stress. When the child had a communication or intellectual impairment or moderate-to-severe pain, parental stress was higher. Khanna et al. examined psychological burden for 204 parents of children with serious chronic conditions. This study found that 75% of parents reported depression, and 67% had anxiety. We are interested in exploring whether adding a skill (Reiki) aimed at decreasing symptoms in the adolescent will result in a decrease in symptoms and chronic stress for the parent.

Teaching parents Reiki has the potential to impact both the child and the parent. Studies with adults have found that professionally-delivered Reiki decreased pain, anxiety, and other symptoms. Parents like to feel empowered in caring for their very ill children and doing so may decrease parental stress and other symptoms. Reiki is non-invasive and can therefore be used with anyone. The National Center for Complementary and Integrative Health (NCCIH) considers Reiki to be safe, although little scientific evidence exists about the effectiveness of Reiki. The proposed study addresses NINR priorities of advancing symptom science to “develop [and] test ... novel, scalable symptom management interventions, including CHAs, in real-world clinical settings to improve health outcomes and quality of life”15(p.15) and the science of compassion to improve palliative and end-of-life care through “developing, testing, and implementing personalized, culturally congruent, and evidence-based palliative and hospice interventions . . . that best address the needs of underserved, disadvantaged, and diverse populations across the care continuum.”15(p. 31) A long-term bonus of teaching parents to deliver Reiki is that Reiki is highly scalable and once learned, costs nothing to use, an important potential overall cost savings over other CHAs.

## 2 Aims and Objectives

**AIM 1.** Establish the feasibility and acceptability of teaching parents Reiki in the home to use with their adolescent receiving palliative care.

**AIM 2.** Explore adolescents' and parents' stress response and symptom profile (i.e., physical function, anxiety, depression, fatigue, sleep, social roles, pain level, and biologic hair and saliva markers).

**AIM 3.** Explore parents' confidence in delivering Reiki and beliefs in their ability to help their adolescent.

We will achieve these aims by enrolling 12 community-dwelling adolescent-parent dyads receiving palliative care at home. Teaching parents Reiki is highly innovative and may provide a novel, easily scalable method of promoting self-management of symptoms.

## 3 Study Design

This study is a mixed methods quasi-experimental one group design.

Parents of hospitalized ill children have been successfully taught to do Reiki with their children.

However, no study that we are aware of has taught parents of community-dwelling children or adolescents receiving palliative care, nor has any study taught parents of these adolescents in a prospective, scientific manner. As such, a one-group feasibility, acceptability study design is appropriate to examine teaching parents Reiki one-on-one in the home using a short teaching period and booster session. The design and sample size will achieve the goals of the study, including preliminary symptom outcome measures and parental feelings about learning Reiki and providing this intervention to their adolescents.

### 3.1 Study population

Adolescent-parent dyads will be recruited in three ways: (1) at an outpatient appointment with the palliative care team; (2) during an inpatient hospitalization; or (3) by mailing a letter, pamphlet, and opt-in/opt-out postcard or emailing a letter and pamphlet to the parent and follow-up with up to three phone calls or emails to introduce the study. For two parent households, parents will need to decide which parent provides at least some care for the adolescent and will perform the bulk of the Reiki sessions. The parent will provide written consent and the adolescent will provide written or verbal assent if able. If the adolescent is developmentally delayed he/she may not be asked to provide written assent/consent. The decision of documented assent/consent will be determined by the judgment of the parent in conjunction with the clinical judgment of the Palliative Care Center. Whenever developmentally appropriate, the adolescent's assent/consent should be solicited through simple explanations, questions, and cues and his/her refusal respected.

#### 3.1.1 Eligibility criteria

Participants will include adolescent-parent dyads receiving care through a palliative care service. We are using the World Health Organization definition of adolescent of ages 10-19 years. We will refer to this age group as adolescent throughout this protocol. Dyads will be **included** if the adolescent: (1) is 10 to 19 years old; (2) understands English; (3) has a prognosis of at least 2 months; and (4) if the parent/legal guardian provides at least some care for the adolescent most days of the week and is able to read and write English at the 8th grade level. Dyads will be **excluded** if (1) either the adolescent or the parent are taking or have taken any form of corticosteroids within the last 30 days (affects the HCC levels), or (2) either the adolescent or the parent has less than one inch of hair. Dyads will also be **excluded** if the adolescent resides in an inpatient facility, is in foster care/custody, or if the dyad does not have reliable means of storing samples at or below 32 degrees Fahrenheit.

We intend to enroll participants regardless of sex, gender, or race. However, the sample size will be too small to analyze results based on these characteristics.

### 3.1.2 Enrollment Details

We will recruit parent-adolescent dyads who fit the inclusion/exclusion criteria. All adolescents will have a life-threatening or life-limiting illness and will be receiving palliative care. Some of the adolescents will be cognitively and/or developmentally delayed and will not be able to give assent to the study. Parents of these adolescents are very aware of their adolescent's moods and symptoms and will choose to consent or not for the study with the best interest of their adolescent in mind. Data will be collected either on paper or using an iPad, depending on the participant preference and/or internet availability. Data will be collected either face-to-face (in the home or during an outpatient visit) or by phone depending on data to be collected and participant preference.

### 3.2 Study measures and outcomes

Table 1: Measures and Timing

Variable (source) # = adolescent, * = parent	T0: Enrollment	T1: End of Intervention	T2: 4-week Follow up
Demographics##	X		
PROMIS Pediatric Global Health 7+2 or Parent Proxy Global Health 7+2#	X	X	X
PROMIS Pediatric Pain Interference or Parent Proxy Pain Interference#	X	X	X
Parent: (physical and emotional) PROMIS 29 Symptom Profile*	X	X	X
Hair Sample Collection##	X		X
Parent Experience of Providing Reiki*			X
Saliva collection##	Pre/post 2 Reiki sessions per week during weeks 1-4		
Medication Log#	Completed during weeks 0-4		
Parent intervention Log*	Completed during weeks 1-4		

Demographic form (T0) basic demographic information on both parent and adolescent.

Patient Reported Outcomes Measurement Information System (PROMIS), sponsored by the NIH. *PROMIS Pediatric Pain Interference* or *PROMIS Parent Proxy SF Pain Interference*, assesses how pain interferes with daily life for the adolescent. Well-validated measures show significant correlations between child and parent reports of pain. We will use the *PROMIS Pediatric Global Health 7+2* measure to obtain an overall evaluation score of the adolescents' physical and mental health. Both self-report and parent proxy versions are valid and reliable. Adult profile PROMIS 29 Symptom Profile (parent) assesses seven domains (depression, anxiety, physical function, pain interference, fatigue, sleep disturbance and ability to participate in social roles and activities).

Medication Log documenting all pain medications given one week prior to and during the intervention period.

Parent Intervention Log provided for parent record keeping. These logs will document Reiki session details, including the date, time, and length of session, interruptions to session, where the session took place, and parent comments and reactions (including adolescent reactions).

Hair collection and assay: Hair cortisol concentration (HCC) is a measure of chronic stress. A recent study found that the mean cortisol level assayed in 1 cm of hair was correlated ( $r=0.61$ ,  $p<0.01$ ) with the mean

salivary cortisol. A four-week follow-up period was chosen in order to obtain an accurate measure of HCC to determine any change in stress during the intervention period. Approximately 10-75 mg of hair is cut from the posterior vertex region of the scalp as close to the scalp as possible. The posterior vertex has the lowest variation in cortisol levels, and is the preferred area for sampling. Co-I ([name]) will train the PI and Co-I ([name]) on hair collection. We will take one cut at the first home visit (T0) and another at the four-week follow-up home visit (T2). Assay: Each 1 cm of hair approximates the mean cortisol level over the prior 1 month. Samples are assayed in duplicate and inter- and intra-assay coefficients of variation calculated. HCC levels are expressed in hair as pg/mg.

Saliva collection and assay: Salivary alpha amylase (sAA) is a non-invasive biomarker that detects immediate changes in autonomic nervous system response, signaling a change in level of stress. Interventional studies have shown a decrease in sAA levels as a response to an intervention meant to stimulate relaxation. Collection: The Salimetrics Drool Tube for adults will be used for saliva collection from the parents and cognitively aware adolescents. The SalivaBio Swab for infants will be used for the remaining adolescents to eliminate any choking hazards. Samples will be collected for both parent and adolescent pre and post two Reiki sessions per week for four weeks. Storage: The swab will be placed in a Swab Storage Tube. Tubes will be put into a sealable plastic bag marked as parent or adolescent, the date and time of collection, and put into the home freezer until the PI or other team member collects them at the follow up visit. Samples will be transported on dry ice to the lab, and frozen at -20C until processed. Assay: The saliva samples will be batch processed after thawing using the Salimetric Alpha Amylase assay following manufacturer's instructions. The amount of alpha-amylase activity present in the saliva sample is directly proportional to the increase in absorbance at 405 nm.

The primary outcome for the proposed study is the feasibility and acceptability of teaching Reiki to parents of adolescents receiving palliative care. Secondary outcomes include: adolescent global health, pain interference, medication use, and stress measures of hair cortisol (chronic, long term) and alpha amylase (immediate, short term); and parent symptom profile (depression, anxiety, physical function, pain interference, fatigue, sleep disturbance and ability to participate in social roles and activities), and stress measures of hair cortisol (chronic, long term) and alpha amylase (immediate, short term).

Because Reiki has not been taught to parents of adolescents receiving palliative care at home, we will determine the feasibility and acceptability of this intervention through calculating the percentage of dyads approached to the total participants who consented to participate in the study as well as completed the study. We will also conduct qualitative interviews with parents to examine what they thought of the teaching protocol, the usefulness of Reiki for stress and other symptoms, as well as their thoughts on the study as a whole. Secondary outcomes will be collected in order to explore preliminary evidence on overall health and quality of life as well as medication use for the adolescents and overall quality of life and symptoms of the parent.

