### **3.2.1 Study events description**

Dyads will be in the study for a total of nine weeks from enrollment to the follow-up visit. Screening occurs at least weekly and prior to enrollment. Enrollment and initial study measure completion, including first hair sample collection from both parent and adolescent, will occur at the beginning of Week 0. Parents will fill out the Medication Log during Week 0 in order to have a baseline of pain and anxiety medications before study intervention begins. The parent will receive Reiki training, a poster with suggested hand positions and a commercially-available book about Reiki in the home on the first day of Week 1. A visit window is defined as a week (7days) -1/+3 days from the initial Reiki training. During Week 2 the parent will receive a Reiki booster session with a repeat of the training and may ask questions. The parent will administer at least 5 times per week for at least 10 minutes each session. During weeks 1-4, the parent will collect saliva samples for themselves and their adolescent before and after any two Reiki sessions as long as they are collected on two separate days. At the end of Week 4, measures will be repeated either in person or by phone. During Week 8, measures will be repeated, the second hair sample obtained from both parent and adolescent, and the parent will participate in a qualitative interview. The qualitative interview will be administered in person by trained OSU College of Nursing

study staff as part of the interview session. Interviews will be audio recorded using a hand-held audio recording device. Audio recordings will be transcribed verbatim. Audio recording is voluntary and participants can choose to not have their interview recorded and still be a part of the study. See Appendix 2 for schema.

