### **3.2.2 Exposure/Outcome measures and instruments**

The main data collection will occur during enrollment (T0), end of the intervention period, Week 4 (T1), and the follow up visit in Week 8 (T2). Parents will be instructed on how to collect and store alpha amylase saliva samples for themselves and their adolescent. Collection: The Salimetrics Drool Tube for adults will be used for saliva collection from the parents and cognitively aware adolescents. The SalivaBio Swab for infants will be used for the remaining adolescents to eliminate any choking hazards. Samples will be collected for both parent and adolescent pre and post any two Reiki sessions on two separate days per week for four weeks. Storage: The swab will be placed in a Swab Storage Tube. Tubes will be put into a sealable plastic bag marked as parent or adolescent, the date and time of collection, and put into the home freezer until the PI or other team member collects them at the follow up visit. Samples will be transported on dry ice to the lab, and frozen at -20C until processed.

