## 4 Statistics and Data Handling

### 4.1 Statistical considerations

Primary outcomes (Aims 1): Feasibility will be examined by computing the proportion of approached subjects enrolled in the study, the proportion of subjects who complete Reiki training, and the proportion of enrolled subjects' who completed data collection. Qualitative data will be analyzed using a basic qualitative descriptive approach. Qualitative data (audio recorded interviews and field notes) will be transcribed verbatim, checked for accuracy, imported into Atlas.TI for data management, and analyzed. Portions of text are labeled or coded with terms that are descriptive of the user opinions and observations. Codes will be identified and defined in an iterative process by investigators independently coding the data and arriving at agreement in discussion/review. Codes are sorted and categorized into themes, which will be discussed in research meetings. We will use mixed methods to triangulate the qualitative and quantitative data to produce a more accurate picture of parental beliefs and experiences. These results will be used to refine procedures for future, larger studies. Qualitative results will be triangulated with quantitative results to answer questions of feasibility. Qualitative results will also be examined to explore the parents' confidence in delivering Reiki and beliefs in their ability to help their adolescent (Aim 3).

Secondary outcomes (Aim 2): Descriptive statistics will be used to check data distribution, identify outliers, examine the balance in baseline measurements, and report outcome measures (e.g. pain) at each time point. Trend plot will be used to visualize the trend of change over time. Pair-wise comparisons will be conducted to test the difference in the change in outcome measures (T0 versus T1, T1 versus T2, T0 versus T2) using two sample t-tests. We will not adjust for multiple comparisons to avoid further reduction of power. Mixed effect modeling for repeated measures will be used to examine the trajectories of treatment effect over time, adjusting for within-patient clustering from repeated measures and possible confounders.

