# 6 Safety Considerations

## 6.1 Risks

The risk of participating in this study are minimal. Reiki is non-invasive and can therefore be used with anyone. NCCIH considers Reiki to be safe although little scientific evidence exists about its effectiveness. There is the possibility that either the parent or adolescent may become uncomfortable during the Reiki session. If this happens, they should either take a break or change positions to be more comfortable. There is a risk for becoming tired or having pain due to the adolescent's illness during the Reiki session. If either of these happens, the dyad should take a break and/or change positions to one that is more comfortable. Some of the data collection may be uncomfortable or inconvenient for the parent and/or adolescent. The hair sample collection may cause a slight physical discomfort due to the gentle pull on the hair before cutting and may cause social discomfort if the parent or adolescent feels as though the small bare spot on the scalp where the hair was clipped may show. Any study personnel who will be collecting hair will be trained to perform the sample cut gently and in a spot not likely to show. Collecting the saliva samples may be inconvenient for the parent as two samples must be collected (pre and post) for both the parent and adolescent (four samples total each time) twice per week for four weeks and stored in the home freezer. We will provide pre-labeled sample tubes and baggies so that the parent only has to add the date to each baggie in order to decrease the inconvenience as much as possible.

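### Salivary amylase is sampled only around Reiki sessions in Weeks 1–4, but the only tests stated in 4.1 compare T0, T1 and T2; its pre/post analysis needs to be defined

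*Combined protocol and SAP*

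**What the plan says.** All references are to the combined protocol and SAP.

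- **Role.** Section 3.2 names among the secondary outcomes, once for the adolescent and once for the parent, "stress measures of hair cortisol (chronic, long term) and alpha amylase (immediate, short term".
- **Sampling.** The saliva row of Table 1 has no visit marks, only the note "Pre/post 2 Reiki sessions per week during weeks 1-4". Section 3.2.2 agrees: "pre and post any two Reiki sessions on two separate days per week for four weeks". Section 6.1 gives the burden as "four samples total each time) twice per week for four weeks". Section 3.2.1 leaves out the weekly qualifier: "before and after any two Reiki sessions as long as they are collected on two separate days".
- **Visits.** Section 3.2.2 defines the main data collection times as "enrollment (T0), end of the intervention period, Week 4 (T1), and the follow up visit in Week 8 (T2".
- **Analysis.** For Aim 2, section 4.1 states the tests as "T0 versus T1, T1 versus T2, T0 versus T2) using two sample t-tests", with no exception for amylase. It also plans descriptive statistics, trend plots, and a repeated-measures mixed model for trajectories over time that allows for clustering within patient and for possible confounders.
- **Size and use.** Section 4.1.1 enrols 12 dyads and says that primary and secondary results will inform the sample size of a later randomized trial.

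**The concern.** Amylase is described as an immediate stress marker, so its natural question is whether it falls from before to after a session. Section 4.1 never states that contrast. The tests it does state compare visits at which no saliva is taken. The test type does not fit either: in a one-group study, comparing two visits compares the same people with themselves, and a two-sample t-test ignores this.

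Families are asked for many tubes, and the result is meant to help plan the next trial. If the analysis is chosen after the data are seen, the p-value and the standard deviation carried forward will depend on how the repeated pairs happened to be combined. Some obvious workarounds have error rates far from nominal.

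**Working it through.** The plan gives no alpha, power, effect size or standard deviation behind its 12 dyads, so there is no figure of its own to reproduce.

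**1. Schedule against stated tests** (Table 1 and section 4.1)

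| Outcome | When collected | Stated visit contrasts with data |
|---|---|---|
| PROMIS measures | T0, T1, T2 | all three |
| Hair cortisol | T0, T2 | T0–T2 only |
| Amylase | session pairs, Weeks 1–4 | none |
| Medication log | Weeks 0–4 | none at T2; Week 0 against Weeks 1–4 is possible |

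No saliva is taken before the Week 1 training or at Week 8. Week 4 tubes are session samples near T1, not a T1 measure.

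**2. Counts** (per-week reading of Table 1, 3.2.2 and 6.1; 12 dyads from 4.1.1)

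- Pairs per person: 2 × 4 = 8. Samples per person: 8 × 2 = 16.
- Samples per dyad: 16 × 2 = 32. Samples in all: 32 × 12 = 384.
- Pairs per role: 12 × 8 = 96, from 12 people.

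**3. Illustration: what happens if the pairs are pooled**

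The documents give no variance components, so the following are assumptions: no pre/post effect, two-sided 5% level, 12 people with 8 pairs each. ICC is the share of the variance of the post-minus-pre difference that is due to person-specific change. Simulations used 40,000 trials per setting.

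*(a) One-sample t-test on 96 pooled differences.* Design effect DEFF = 1 + (8 − 1) × ICC; approximate type I error = 2 × [1 − Φ(1.96/√DEFF)].

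| ICC | DEFF | Effective pairs (96/DEFF) | Formula | Simulated |
|---|---|---|---|---|
| 0 | 1.0 | 96 | 0.05 | 0.05 |
| 0.1 | 1.7 | 56 | 0.133 | 0.13 |
| 0.3 | 3.1 | 31 | 0.266 | 0.27 |
| 0.5 | 4.5 | 21 | 0.356 | 0.37 |

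*(b) Two-sample t-test on 96 pre against 96 post tubes.* Two errors oppose each other: ignoring the pairing makes the test conservative, and ignoring person-specific change makes it liberal. Simulated type I error as ICC goes from 0 to 0.5:

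- person, session and residual variance 0.6, 0.2, 0.2: 0.0001 to 0.06
- 0.5, 0, 0.5: 0.009 to 0.24
- 0.3, 0.2, 0.5: 0.006 to 0.23
- 0, 0, 1: 0.05 to 0.43

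*(c) One-sample t-test on 12 person means.* Simulated type I error 0.049 to 0.052 in every setting.

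If section 3.2.1 were read literally as two sessions in all, DEFF would be 1 + (2 − 1) × ICC, or 1.1 to 1.5 for ICC 0.1 to 0.5. The inflation in (a) would be milder; the mismatch in step 1 would be unchanged.

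**4. Two-sample test on visit measures** (12 people, no effect, assumed correlation between visits)

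At correlation 0.5 the two-sample t-test rejects 0.9% of the time, and at 0.7 it rejects 0.2%. The paired test rejects about 5% in both cases. For PROMIS and hair cortisol, the stated test would therefore usually discard power.

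**5. What remains after the correction**

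With 12 person means, 80% power needs a mean change of 0.89 standard deviations of those means; with 10 people, 1.00. The mixed model proposed below was not simulated; the person-mean test that serves as its check was.

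**The case against.** The strongest reply is that 4.1 already plans a mixed model under Aim 2 that adjusts for clustering of repeated measures within patient, and that amylase is the most densely repeated biomarker in the study. That sentence is not limited to T0, T1 and T2, and descriptive statistics and trend plots are planned as well. So it would be too strong to infer that amylase has no planned analysis of any kind. This part of the reply stands. What it does not supply is the contrast: the model is described for trajectories over time, with no pre/post term, no session level and no tested parameter for amylase. The remedy refines a method the plan already names.

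A reader might also infer that the plan treats 96 pairs as 96 people, or that its stated test will give wrong amylase p-values. The documents support neither. They are silent on how pairs would be combined, and a test between visits with no saliva gives no amylase p-value at all. The error rates above describe workarounds, not planned analyses. They rest on assumed variances, the inflation in (a) disappears at ICC 0, and the two-sample range moves widely with how the variance is split.

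Finally, the primary outcome is feasibility and acceptability, section 4.1.1 puts the emphasis on Aims 1 and 3, and no decision rule depends on an amylase result. That limits the severity.

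**Conclusion.** The point holds as a gap between schedule and analysis. It can be seen from Table 1 and section 4.1 without any assumption: the stated tests have no amylase data, and a two-sample test is the wrong form for one group measured repeatedly. The mixed model narrows the gap but, as written, does not close it.

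The numbers show why the choice should be made in advance. Simple pooling of differences would run at about 13% to 37% for ICC 0.1 to 0.5, pooled tubes could err in either direction, and person means hold close to 5%. These figures assume 12 people with 8 complete pairs and a two-sided 5% level, which the plan does not state.

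Because amylase is exploratory in a 12-dyad feasibility study, this is a change that should be made before analysis, not one on which the trial's main conclusions depend.

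**What to change.** Add to section 4.1:

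> For sAA, the post-minus-pre change (log scale if the planned distribution check supports it) will be analysed separately for parents and adolescents with a mixed model with a random person intercept, week centred over Weeks 1–4, and small-sample degrees of freedom. The tested parameter is the mean change over Weeks 1–4. Check: one-sample t-test on each person's mean change.

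Week needs centring, at (1 + 2 + 3 + 4)/4 = 2.5. Left uncentred, the intercept would be an extrapolated change at Week 0, before training.

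In the same section, replace the two-sample t-tests with paired, within-person contrasts that follow Table 1:

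- PROMIS measures: T0, T1 and T2.
- Hair cortisol: T0 against T2 only.
- Medication use: Week 0 against Weeks 1–4. It is a secondary outcome and would otherwise be left without a usable test.

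Reconcile the saliva frequency in section 3.2.1 with Table 1, the saliva paragraph of 3.2, section 3.2.2 and section 6.1.

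The cost is analysis wording only. Sampling, visits and enrolment are unchanged. The price in apparent precision is that the effective sample size is openly 12 people per role, not 96 pairs.
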